5.0 STUDY PROCEDURES

5.1 Screening/Baseline Procedures

Assessments performed exclusively to determine eligibility for this study will be done only after obtaining informed consent. Assessments performed for clinical indications (not exclusively to determine study eligibility) may be used for baseline values even if the studies were done before informed consent was obtained.

All screening procedures must be performed within 60 days prior to registration unless otherwise stated. The screening procedures include:

5.1.1 Informed Consent

5.1.2 Medical history

Complete medical and surgical history, history of infections

5.1.3 Demographics

Age, gender, race, ethnicity

5.1.4 Review subject eligibility criteria

5.1.5 Review previous and concomitant medications

Including history of chemotherapy and history of any antibiotic treatment within three months of study enrollment

5.1.6 Physical exam including vital signs, height and weight

Vital signs (temperature, pulse, respirations, blood pressure), height, weight

5.1.7 Performance status

Performance status evaluated prior to study entry according to Appendix A.

5.1.8 Hematology

Complete blood count with differential.

5.1.9 Serum chemistries

Comprehensive metabolic panel (CMP) to include: albumin, alkaline phosphatase, ALT/SGPT, AST/SGOT, BUN, creatinine, electrolytes (sodium, potassium, calcium, chloride, bicarbonate), glucose, and total bilirubin.

5.1.10 Pregnancy test (for females of child bearing potential)

See section 3.1.6.1 for definition.

5.1.11 Tumor assessment

CT or MRI of chest, abdomen, and pelvis with IV contrast, when possible. Additional imaging may be obtained at the treating clinician's discretion. Baseline imaging to determine eligibility must have been obtained within 60 days of trial enrollment.

5.2 Procedures During Treatment

5.2.1 At time of each PULSAR Fraction

- Physical exam, vital signs, history
- Toxicity assessment

5.2.2 At time of radical cystectomy

- Physical exam, vital signs, history
- Toxicity assessment

5.2.3 30 days after radical cystectomy

- Physical exam, vital signs
- Toxicity evaluation
- Hematology (standard of care)
- Serum chemistries (standard of care)

5.2.4 90 days after radical cystectomy

- Physical exam, vital signs
- Toxicity evaluation
- Hematology (standard of care)
- Serum chemistries (standard of care)
- Restaging imaging (standard of care)

5.2.5 Every 6 months x 2 years

- Chart review and/or patient contact to determine recurrence and vital status

5.3 Follow-up Procedures

Subjects will be followed at the 30 and 90 day timepoints (\pm 4 weeks) following radical cystectomy. After that time frame, patients will be followed

- Procedure

5.4 Time and Events Table

	Screening	PULSAR Q12-16d x 3 fractions	Post PULSAR, pre RC	Post RC (30 days)	Post RC (90 days)	Follow up q6mo x 2 yrs
Procedures						
Informed Consent	X					
Eligibility verification	X					
History and Physical Exam	X	X	X	X	X	
Performance Status	X	X	X	X	X	
(Re)staging Imaging ¹	X		X		X	
Toxicity Evaluation		X	X	X	X	
Blood Draw ²	X	X	X	X	X	

Pregnancy Test (if applicable) ³	X					
PULSAR treatment ⁴		X				
Chart review / recurrence status						X

¹ CT or MRI with IV contrast, if possible. Imaging to determine eligibility must have been performed within **60 days of enrollment**. All imaging used within the study represents standard of care. Additional imaging may be obtained at the treating clinician's discretion.

² Blood draws after surgery represent standard of care

³ Only in females of child-bearing potential, as defined in section 3.1.

⁴ SAbR treatments to be administered in three fractions at 12-16 day intervals.

5.5 Removal of Subjects from Study

Subjects can be taken off the study treatment and/or study at any time at their own request, or they may be withdrawn at the discretion of the investigator for safety, behavioral or administrative reasons. The reason(s) for discontinuation will be documented and may include:

- 5.5.1 Subject voluntarily withdraws from treatment (follow-up permitted);
- 5.5.2 Subject withdraws consent (termination of treatment and follow-up);
- 5.5.3 Subject is unable to comply with protocol requirements;
- 5.5.4 Subject demonstrates disease progression (unless continued treatment with study drug/treatment is deemed appropriate at the discretion of the investigator);
- 5.5.5 Subject experiences toxicity that makes continuation in the protocol unsafe;
- 5.5.6 Treating physician judges continuation on the study would not be in the subject's best interest;
- 5.5.7 Subject becomes pregnant (pregnancy to be reported along same timelines as a serious adverse event);
- 5.5.8 Development of second malignancy (except for basal cell carcinoma or squamous cell carcinoma of the skin) that requires treatment, which would interfere with this study;
- 5.5.9 Lost to follow-up. If a research subject cannot be located to document survival after a period of 2 years, the subject may be considered "lost to follow-up." All attempts to contact the subject during the two years must be documented and approved by the Data Monitoring Committee.

6.0 MEASUREMENT OF EFFECT

6.1 Antitumor Effect

Response and progression following radical cystectomy (as distinct from criteria for trial eligibility, which are defined in section 3.1.2 above), will be evaluated in this study using the new international criteria proposed by the Response Evaluation Criteria in Solid Tumors (RECIST v 1.1) Committee [Eur J Cancer. 2009;45(2):228-247]. Changes in only the largest diameter (unidimensional measurement) of the tumor lesions are used in the RECIST v1.1 criteria.

6.1.1 Definitions

Evaluable for toxicity. All subjects will be evaluable for toxicity from the time of their first treatment with PULSAR.

Evaluable for objective response. Only those subjects who have measurable disease present at baseline, have received at least one PULSAR treatment, and have had their disease re-evaluated will be considered evaluable for response. These subjects will have their response classified according to the definitions stated below. (Note: Subjects who exhibit objective disease progression prior to the end of treatment will also be considered evaluable.)

6.1.2 Disease Parameters

Measurable Disease: Tumor lesions: Must be accurately measured in at least one dimension (longest diameter in the plane of measurement is to be recorded) with a minimum size of:

1. 10 mm by CT scan (CT scan slice thickness no greater than 5 mm)
2. 10 mm caliper measurement by clinical exam (lesions which cannot be accurately measured with calipers should be recorded as non-measurable)
3. 20 mm by chest x-ray.

Malignant lymph nodes: To be considered pathologically enlarged and measurable, a lymph node must be ≥ 15 mm in short axis when assessed by CT scan (CT scan slice thickness recommended to be no greater than 5 mm).

Lymph nodes merit special mention since they are normal anatomical structures which may be visible by imaging even if not involved by tumor. Pathological nodes which are defined as measurable and may be identified as target lesions must meet the criterion of a short axis of ≥ 15 mm by CT scan. Only the short axis of these nodes will contribute to the baseline sum. The short axis of the node is the diameter normally used by radiologists to judge if a node is involved by solid tumor. Nodal size is normally reported as two dimensions in the plane in which the image is obtained (for CT scan this is almost always the axial plane; for MRI the plane of acquisition may be axial, sagittal or coronal). The smaller of these measures is the short axis. For example, an abdominal node which is reported as being 20 mm x 30 mm has a short axis of 20 mm and qualifies as a malignant, measurable node. In this example, 20 mm should be recorded as the node measurement. All other pathological nodes (those with short axis ≥ 10 mm but < 15 mm) should be considered non-target lesions. Nodes that have a short axis < 10 mm are considered non-pathological and should not be recorded or followed.

Note: Previously irradiated lesions are non-measurable except in cases of documented progression of the lesion since the completion of radiation therapy. For this reason, and because of the potential for pseudoprogression as discussed above, the pelvic lymph nodes will not be considered evaluable at the initial restaging scan following PULSAR and prior to radical cystectomy.

Non-measurable disease.

All other lesions are considered non-measurable, including small lesions (longest diameter < 10 mm or pathological lymph nodes with ≥ 10 to < 15 mm short axis) as well as truly non-measurable lesions. Lesions considered truly non-measurable include: leptomeningeal disease, ascites, pleural or pericardial effusion, inflammatory breast disease, lymphangitic involvement of skin or lung, abdominal masses/abdominal organomegaly identified by physical exam that is not measurable by reproducible imaging techniques.

Target lesions.

All measurable lesions up to a maximum of five lesions total (and a maximum of two lesions per organ) representative of all involved organs should be identified as target lesions

Non-target lesions. All other lesions (or sites of disease) including any measurable lesions over and above the five target lesions should be identified as **non-target lesions** and should also be recorded at baseline. Measurements of these lesions are not required, but the presence or absence of each should be noted throughout follow-up.

6.1.3 Methods for Evaluation of Measurable Disease

All measurements should be taken and recorded in metric notation using a ruler or calipers. All baseline evaluations should be performed as closely as possible to the beginning of treatment and not more than 60 days before the beginning of the treatment.

The same method of assessment and the same technique should be used to characterize each identified and reported lesion at baseline and during follow-up. Imaging-based evaluation is preferred to evaluation by clinical examination when both methods have been used to assess the antitumor effect of a treatment.

Conventional CT and MRI. These techniques should be performed with cuts of 10 mm or less in slice thickness contiguously. Spiral CT should be performed using a 5 mm contiguous reconstruction algorithm. This applies to tumors of the chest, abdomen, and pelvis.

Cytology, Histology. These techniques can be used to differentiate between partial responses (PR) and complete responses (CR) in rare cases (e.g., residual lesions in tumor types, such as germ cell tumors, where known residual benign tumors can remain).

The cytological confirmation of the neoplastic origin of any effusion that appears or worsens during treatment when the measurable tumor has met criteria for response or stable disease is mandatory to differentiate between response or stable disease (an effusion may be a side effect of the treatment) and progressive disease.

6.1.4 Response Criteria

6.1.4.1 Evaluation of Target Lesions

Complete Response (CR): Disappearance of all target lesions. Any pathological lymph nodes (whether target or non-target) must have reduction in short axis to <10 mm (the sum may not be "0" if there are target nodes). Determined by two separate observations conducted not less than 4 weeks apart. There can be no appearance of new lesions.

Partial Response (PR): At least a 30% decrease in the sum of the longest diameter (SLD) of target lesions, taking as reference the baseline SLD. There can be no appearance of new lesions.

Progressive Disease (PD): > 20% increase in the SLD taking as reference the smallest SLD recorded since the treatment started (nadir) and minimum 5 mm increase over the nadir.

Stable Disease (SD): Neither sufficient shrinkage to qualify for PR nor sufficient increase to qualify for PD, taking as reference the smallest SLD since the treatment started. There can be no unequivocal new lesions.

While on study, should a chosen Target lesion become non-evaluable, document as Not Evaluable (NE).

6.1.4.2 Evaluation of Non-Target Lesions

Complete Response (CR): Disappearance of all non-target lesions and normalization of tumor marker level. All lymph nodes must be non-pathological in size (< 10 mm short axis).

(Non-CR/Non-PD): Persistence of one or more non-target lesion(s) and/or maintenance of tumor marker level above the normal limits.

Progressive Disease (PD): Appearance of one or more new lesions and/or unequivocal progression of existing non-target lesions.

While on study, should a chosen Non-Target lesion become non-evaluable, document as Not Evaluable (NE).

6.1.4.3 Evaluation of Best Overall Response

The best overall response is the best response recorded from the start of the treatment until disease progression/recurrence (taking as reference for progressive disease the smallest measurements recorded since the treatment started). The subject's best response assignment will depend on the achievement of both measurement and confirmation criteria.

Time point response: patients with target (+/- non-target) disease.			
Target lesions	Non-target lesions	New lesions	Overall response
CR	CR	No	CR
CR	Non-CR/non-PD	No	PR
CR	Not evaluated	No	PR
PR	Non-PD or not all evaluated	No	PR
SD	Non-PD or not all evaluated	No	SD
Not all evaluated	Non-PD	No	NE
PD	Any	Yes or No	PD
Any	PD	Yes or No	PD
Any	Any	Yes	PD

CR = complete response, NE = not evaluable, PD = progressive disease, PR = partial response, SD = stable disease.

Time point response: patients with non-target disease only.		
Non-target lesions	New lesions	Overall response
CR	No	CR
Non-CR/non-PD	No	Non-CR/non-PD
Not all evaluated	No	NE

Uequivocal PD	Yes or No	PD
Any	Yes	PD

CR = complete response, NE = not evaluable, PD = progressive disease

A 'Non-CR/non-PD' is preferred over 'stable disease' for non-target disease since SD is increasingly used as endpoint for assessment of efficacy in some trials so to assign this category when no lesions can be measured is not advised.

6.1.5 Duration of Response

Duration of overall response: The duration of overall response is measured from the time measurement criteria are met for CR or PR (whichever is first recorded) until the first date that recurrent or progressive disease is objectively documented (taking as reference for progressive disease the smallest measurements recorded since the treatment started).

The duration of overall CR: The duration of overall CR is measured from the time measurement criteria are first met for CR until the first date that recurrent disease is objectively documented.

Duration of stable disease: Stable disease is measured from the start of the treatment until the criteria for progression are met, taking as reference the smallest measurements recorded since the treatment started.

6.1.6 Progression-Free Survival

Progression-free survival (PFS) is defined as the duration of time from start of PULSAR treatment to time of progression. Progression is defined as any of:

1. Radiologic disease progression, as defined by RECIST 1.1 criteria above.
2. Pathologic demonstration of recurrent or metastatic disease (e.g. core needle biopsy, fine needle aspirate, diagnostic peritoneal lavage).
3. Initiation of a patient on salvage or palliative treatment due to clinical concern for disease progression.
4. For patients with documented concern (by the operating surgeon) for grossly incomplete disease resection (R2) including bulky unresectable lymph nodes, the date of the first postoperative imaging study showing disease progression by RECIST 1.1 criteria.

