From the preceding data it is apparent that patients with cN+ bladder cancer who are ineligible for or who fail to respond to downstaging chemotherapy are an unfortunate group with particularly poor outcomes. One potential avenue for improvement is the combination of stereotactic ablative radiotherapy (SAbR) and immune checkpoint inhibitor (ICI) as downstaging therapy prior to radical cystectomy. We anticipate that patients will benefit from the demonstrated anti-tumor effects of both treatment modalities. Additionally, combining the immunomodulatory effects of SAbR with the stimulatory effects of ICI may result in a synergistic effect more beneficial than either modality alone.

1.2 Stereotactic Ablative Radiotherapy (SAbR) and Personalized Ultrafractionated Stereotactic Adaptive Radiotherapy (PULSAR)

Stereotactic Ablative Radiation (SAbR), also known as Stereotactic Body Radiation Therapy (SBRT), is defined by the American Society of Radiation Oncology as a precise and specialized form of cancer treatment “whereby high doses of radiation are delivered

in large fraction sizes over a short course of treatment, generally limited to 5 or fewer fractions.”¹⁶ Metastasis-directed therapy with SAbR has attracted interest in a variety of malignancies due to promising early clinical results and a favorable toxicity profile. In the Phase II SABR-COMET trial, patients with cancer (primarily breast, lung, colorectal, and prostate) and up to five sites of metastasis were randomized to receive metastasis-directed SAbR (8-30 Gy in 1-10 fractions) versus standard of care. The use of SAbR resulted in an improvement in 5-year overall survival from 18% to 42% ($p = 0.006$) and in 5-year progression-free survival from ~3% to 17% ($p = 0.001$)¹⁷. Grade ≥ 2 adverse events were noted in 29% of patients and treatment-related deaths in 4.5%¹⁸.

In the Phase II ORIOLE trial, men with prostate cancer and 1-3 sites of metastatic disease were randomized to receive metastasis-directed SAbR (20-48 Gy in 3-5 fractions) versus standard of care. SAbR resulted in improved progression-free survival (median not reached vs 5.8 months, $p = 0.002$) with no grade ≥ 3 toxic events¹⁹. These results of these trials support a significant recurrence-free and overall survival benefit for metastasis-directed SAbR in oligometastatic cancer.

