2.4 Secondary Endpoints

2.4.1 Progression free survival (PFS): Primary disease progression will be defined as any of the following. Progression-free survival will be measured from the date of the first PULSAR treatment.

1. Emergence of new sites of disease or locoregionally recurrent disease as defined by RECIST 1.1 criteria.

2. Pathologic demonstration of recurrent or metastatic disease (e.g. core needle biopsy, fine needle aspirate, diagnostic peritoneal biopsy).
3. Initiation of a patient on palliative or salvage treatment due to clinical concern for disease progression.
4. For patients with intraoperative concern for grossly incomplete disease resection (R2), the date of the first postoperative imaging study showing disease progression by RECIST 1.1 criteria (i.e., 20% increase in the sum of the diameters of all lesions, with an absolute increase of at least 5 mm; or the appearance of any new lesion).

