4.11 Duration of Follow Up

All follow up after radical cystectomy represents the standard of care. Patients will be followed for adverse outcomes for 90 days following radical cystectomy. After that point, subjects will only be followed for progression-free and overall survival for two years from the date of first PULSAR treatment or disease recurrence, whichever occurs first.

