9.2 Sample Size and Accrual

For the primary endpoint of feasibility, we define a target rate of protocol completion (completion of radical cystectomy within sixteen weeks of initiation of PULSAR) of 90%, with a lower boundary of futility at 60%. A sample size of 24 patients provides 91% power to reject a 60% completion rate at a two-sided alpha of 0.05. Of note, this sample size was employed in the recent NABUCCO trial, which addressed a similar high-risk patient cohort³⁶. Allowing a 10% drop out rate increases the desired enrollment to a total of **27 patients**. Given the desired enrollment of 27 patients and the three-year trial period, this will require accrual of nine patients per year across all sites.

For the secondary endpoint of progression-free survival, the trial-eligible subset of our recently published historic series of cN+ bladder cancer patients achieved a 2-year recurrence-free survival rate of 30%¹⁵. A sample size of 24 patients provides 90% power to detect a 27% absolute increase in 2-year recurrence free survival with a one-sided alpha of 0.10 using the Kaplan-Meier log-rank test.

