9.3 Data Analyses

The primary endpoint, protocol completion, will be assessed by calculating the proportion of patients completing radical cystectomy within sixteen weeks of initiating PULSAR treatment. If the proportion of patients undergoing cystectomy exceeds 60%, the null hypothesis (that use of ICI+PULSAR+RC is not feasible) will be deemed to have been rejected.

For the secondary endpoint, progression-free survival will be determined as described above, and will be reported by means of Kaplan-Meier survival curves, median progression-free survival time, and proportion of patients without progression at two years. Comparison will be made to the trial-eligible subset of patients in a historic control series using the log-rank test. The 2-year progression-free survival rate in the historic cohort was 30%. The null hypothesis will be rejected if the one-sided *p* value for the comparison is less than 0.10.

Additional planned analyses include the following, all of which will be reported with simple descriptive statistics (*n* / *N* and percentage):

Major complication rate: A major surgical complication will be defined as any postoperative complication of Clavien-Dindo Grade III or higher.

Pathologic outcomes: Pathologic outcomes will be defined as follows, based on the final surgical pathology report:

1. Pathologic complete response: no viable disease remaining in the specimen (ypT0 N0).
2. Pathologic non-muscle-invasive downstaging: primary tumor without muscle invasion, and no viable disease in lymph nodes (\leq ypT1 N0).
3. Pathologic organ-confined downstaging: primary tumor confined to detrusor muscle, and no viable disease in lymph nodes (\leq ypT2 N0).
4. Nodal complete response: no viable disease in lymph nodes, regardless of primary tumor stage (ypTany N0).

Residual disease: Residual disease at surgery will be defined as follows:

1. Microscopic residual disease (R1) will be defined as any positive soft tissue margin on the final surgical pathology report, excluding carcinoma *in situ* at ureteral margins.
2. Gross residual disease (R2) will be defined as any grossly positive tissue margin reported on a pathology report, *or* the operating surgeon's subjective report of grossly unresectable disease including bulky matted lymph nodes.

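### The PFS definition omits death, so a patient who dies without progression is not a failure in the only powered efficacy comparison

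*Combined protocol and SAP*

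**What the plan says.** Section 2.4.1 measures PFS from the first PULSAR treatment and introduces its event list with "Primary disease progression will be defined as any of the following". Four kinds of event follow: new or locoregionally recurrent disease on imaging, pathologic proof of disease, the start of salvage or palliative treatment for suspected progression, and imaging progression after a grossly incomplete resection. Section 6.1.6 has the same structure: "Progression-free survival (PFS) is defined as the duration of time from start of PULSAR treatment to time of progression", followed by four progression items. Death is in neither list, and the RECIST tables in section 6.1.4 do not classify death as progression.

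Section 9.3 adds no further rule: "progression-free survival will be determined as described above". It reports the "proportion of patients without progression at two years" and tests against the historic series at one-sided 0.10. Sections 9.1 and 9.2 call the endpoint recurrence-free survival without defining that term. Section 9.2 says the historic series "achieved a 2-year recurrence-free survival rate of 30" per cent, and section 9.3 gives the same 30% as PFS.

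Deaths are observed. Section 4.11 says that "subjects will only be followed for progression-free and overall survival for two years", and section 5.2.5 schedules "Chart review and/or patient contact to determine recurrence and vital status" every six months for two years. Section 9 plans no analysis of overall survival.

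**The concern.** PFS ordinarily ends at progression or death from any cause. Here the protocol writes out a closed definition twice, and death is missing both times. An analyst who follows the text has no basis for scoring a death as an event. An analyst who follows convention departs from the text. The two analyses can differ, and the plan does not choose between them.

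This comparison is the trial's only powered test of efficacy (24 patients, 90% power, 30% against 57% at two years). The error has one direction: leaving out a death before two years can raise the reported rate but never lower it.

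Such deaths are plausible. Every patient is planned for checkpoint inhibition, ablative radiotherapy and radical cystectomy, and Cohort 1 includes patients medically unfit for platinum. The last scheduled restaging scan is 90 days after cystectomy, so a later cancer death could also occur with no documented progression.

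Other parts of the plan record some of these deaths: the primary endpoint (before cystectomy), the 90-day Clavien-Dindo complications, and SAE reporting. None of these is a survival estimate, so a death without progression counts against the regimen in no planned survival analysis.

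**Working it through.** **The plan's own figure.** Inputs from section 9.2: n = 24, historic rate 0.30, alternative 0.30 + 0.27 = 0.57, one-sided alpha 0.10, power 90%. An exact binomial rule that rejects at 11 or more of 24 event-free has alpha 0.074 and power 0.904. The stated 90% is therefore reproduced and is not in dispute. Adding death as an event leaves it unchanged, provided the historic 30% also counts deaths.

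**Effect of one death.** Take 27 patients, 19 failures, 8 event-free and no other censoring. Kaplan-Meier gives 8/27 = 29.6%. If one failure is instead a censored death with k patients at risk, the factor (k-1)/k drops out and the estimate is multiplied by k/(k-1):

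- k = 27: 29.63 x 27/26 = 30.77, +1.1 points
- k = 15: 29.63 x 15/14 = 31.75, +2.1 points
- k = 9 (last event): 29.63 x 9/8 = 33.33, +3.7 points

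If the patient is counted as progression-free, the gain is 1/27 = 3.7 points whenever the death occurs.

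**Illustrative rate.** The only treatment-death rate in the documents is in section 1.2, for a trial of metastasis-directed radiotherapy: "treatment-related deaths in 4.5" per cent. That trial enrolled other cancers and involved no cystectomy, so the rate is an illustration only.

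- Expected deaths: 27 x 0.045 = 1.2.
- Expected failures at a true 30%: 27 x 0.70 = 18.9.
- Share of failures that are such deaths: f = 1.2/18.9 = 0.064.
- Deaths censored, constant hazards: 0.30^(1 - 0.064) = 0.324. If all of them fall in months 2 to 6, the result is 0.317.
- Deaths counted as progression-free: 0.30 + 0.045 = 0.345.

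**Sensitivity.** The larger values of f have no source in the documents. The apparent rate is 0.30^(1 - f). The error column is a two-sample log-rank simulation with 24 trial patients against 30 or 100 historic patients (both sizes assumed), 20,000 runs, nominal one-sided 0.10, and deaths counted **only** in the historic arm.

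| f | Deaths in 27 (27 x 0.70 x f) | A true 30% reads | One-sided error |
|---|---|---|---|
| 0 | 0 | 30.0% | 0.09-0.10 |
| 0.064 | 1.2 | 32.4% | 0.13-0.14 |
| 0.1 | 1.9 | 33.8% | 0.16-0.17 |
| 0.2 | 3.8 | 38.2% | 0.26-0.28 |
| 0.3 | 5.7 | 43.1% | 0.38-0.44 |

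A separate one-sample log-rank simulation against a fixed 30% agrees. If 5%, 10%, 15% or 20% of patients die without progression, the apparent rate is 0.30^(1 - q/0.70), where q is that proportion: 32.7%, 35.6%, 38.8% and 42.3%. The one-sided error is about 14%, 22%, 33% and 45%, against about 9% when deaths count.

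If the historic series also leaves deaths out, the simulated error stays at about 0.08-0.10 throughout and the test is not inflated.

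**The case against.** The strongest points on the other side are these.

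- **The third list item already catches many cancer deaths.** Starting salvage or palliative treatment for suspected progression is an event without imaging or biopsy. This is right, and it limits the gap to deaths with none of the four listed events.
- **The test is inflated only if the historic 30% counted deaths.** This stands. The series is the institution's own, the protocol calls its result both PFS and recurrence-free survival, and its definition is not given. The bias in the reported 2-year rate does not depend on this.
- **The large sensitivity cases have no anchor.** This also stands. Six deaths of this kind in 27 patients with ECOG 0-1 who are fit for cystectomy would be many. At the 4.5% illustration the shift is about 2 to 4.5 points, against a standard error of about 9 points (square root of 0.30 x 0.70/24 = 0.094; with 27 patients, 0.088) and a target difference of 27 points.
- **A progression-only endpoint may be intended.** Section 1.4 treats recurrence as a proxy for cancer-specific survival. That reading conflicts with the name progression-free survival. It would also still need a stated rule for deaths.
- **This is a secondary endpoint.** The primary decision on completion within sixteen weeks is not affected, and it already fails a patient who dies before cystectomy.

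These points limit the size of the problem. None of them puts death back into the definition.

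**Conclusion.** The concern holds. Both definitions are closed lists without death, the analysis section relies on them, and nothing elsewhere restores death as an event. The endpoint is time to progression labelled as PFS, with no rule for patients who die first.

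The size is conditional and requires at least one such death. Each one adds 1.1 to 3.7 points in the 27-patient example. At the illustrative 4.5% rate a true 30% reads as about 32% to 34.5%. The one-sided error rises to about 13-14% at that rate only if the historic series counted deaths. These figures assume constant hazards unless stated and, for the two-sample error rates, assumed historic sample sizes. No stated design number changes. The definition should be corrected before the analysis.

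**What to change.** - In sections 2.4.1 and 6.1.6, write: *PFS runs from the first PULSAR treatment to whichever comes first, progression (items 1-4) or death from any cause; patients alive without progression are censored at their last disease-status assessment.* Use one list in both places, because item 1 is currently worded differently in the two sections.
- In section 9.3, report the Kaplan-Meier proportion alive and without progression at two years.
- Use this one definition and one name throughout sections 9.1 to 9.3, in place of the mix of progression-free and recurrence-free survival.
- Before the log-rank comparison, confirm that the historic series counts deaths in the same way, or re-score it.

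The cost is a few sentences of wording plus a check of the historic series, with re-abstraction if it did not count deaths. No new trial data are needed, because vital status is already scheduled every six months for two years. The reported 2-year rate may be slightly lower than under the current text.
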